10.5. Tabulation of Individual Participant Data

Data will be tabulated in a de-identified fashion, without center or patient identifiers.

10.6. Populations for Analyses

For questions related to the Phase 1 intervention, analyses will use an intent-to-treat (ITT) approach, in which all available data on all randomized participants are included. Participants who discontinue an assigned intervention will be encouraged to remain in the trial to provide complete follow-up data and will be included in the ITT analysis. For participants with missing outcome ascertainment due to withdrawal or other reasons, data from earlier assessments will be used. For example, for the primary objective for Phase 1, if Week 12 outcome data are not available, baseline data will be used.

The characteristics at the time of randomization for those participants without complete follow-up will be examined; however, there will be limited statistical power to detect differences between participants with and without complete follow-up. To assess potential biases introduced by differential withdrawal among the intervention groups, comparisons of withdrawal rates and/or time to withdrawal will be performed as an ancillary analysis to the primary efficacy analysis.

Other populations that may be used in secondary analyses are defined as follows:

- As-treated population: Any participant randomized into the study regardless of whether they received study intervention. As-treated participants will be analyzed according to the study intervention actually received.

- All-treated population: Any participant randomized into the study that received at least some of the study intervention.
- Per-protocol population: Any participant who was appropriately randomized and was exposed to the protocol-dictated study intervention for $\geq 75\%$ of the planned duration and had the outcome assessments through Week 24.

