Each of eight Clinical Centers aims to recruit "m" participants. The University of Washington Clinical Center consists of three recruitment sites: University of Washington, Rogosin Institute, and University of New Mexico. The University of Washington and Rogosin will each recruit 43.75% of the Clinical Center's target, and the University of New Mexico will recruit 12.5% of the target. The University of Pittsburgh Clinical Center consists of two recruitment sites: University of Pittsburgh and University of Pennsylvania. The University of Pittsburgh site will recruit two thirds of the Clinical Center's target and the University of Pennsylvania site will recruit one third of the target. The Vanderbilt Clinical Center consists of two recruitment sites: Vanderbilt University Medical Center and West Virginia University. Vanderbilt University Medical Center will recruit two thirds of the

Clinical Center's target, and West Virginia University will recruit one third of the target. The Yale University Clinical Center consists of three recruitment sites in Veterans Affairs Healthcare Systems; each site will recruit one third of the target. Therefore, there are 14 recruitment sites. When clustering at the recruitment site level is considered in the power calculation, the average cluster size per recruitment site per arm is $\bar{m} = 0.571 \times \frac{m}{2} = 0.286m$, and the standard deviation of cluster size is $s_m = 0.313 \times \frac{m}{2} = 0.156m$. This will yield the design effect of $1 + \text{ICC} \times \left[\left\{ \left(\frac{s_m}{\bar{m}} \right)^2 + 1 \right\} \times \bar{m} - 1 \right]$. For example, for $m = 80$ and $\text{ICC} = 0.02$, \bar{m} is 22.88, s_m is 12.48, and the design effect is 1.574. Thus, the sample size per arm in the power calculation is around $139 \left(\frac{80 \times 8}{2} \times \frac{1}{1.574} \times \{1 - 0.2\} \times \frac{1}{1.173} \cong 139 \right)$ after taking into account the design effect (1.574), the attrition rate (0.2) and the inflation factor of the interim analysis (1.173).

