10.2.2.1. Analyses of the Primary Endpoint for the Phase 1 Randomization

Question 1 (Table 10.1): Does a PCST intervention consisting of weekly, live, coach-led sessions improve outcomes at 12 weeks?

Question 1 addresses the primary trial hypothesis. The primary efficacy endpoint, the change in BPI Interference between baseline and 12 weeks, and will be analyzed using a linear mixed effects model.⁶² The linear mixed effects model will include fixed effects of intervention, time, and interactions between intervention and time, taking into account the repeated measures over time and clustering of recruitment sites via random effects. All repeated measures of the BPI Interference scores at baseline and 12 weeks will be included in the model as the dependent variable. The linear mixed effects model is expressed as

$$y_{ijk} = \beta_0 + \beta_1 X_{ij} + \beta_2 I(T_{ijk} = 12) + \beta_3 X_{ij} I(T_{ijk} = 12) + \gamma^T \mathbf{W}_{ij} + \theta_i + \alpha_{ij} + \varepsilon_{ijk},$$

where y_{ijk} is the BPI Interference score for participant ij ($i = 1, 2, \dots, 14$; $j = 1, 2, \dots, n_i$; n_i is number of participants from recruitment site i) at time point k ($k = 1, 2$), X_{ij} is the binary intervention indicator ($X_{ij} = 1$ if PCST; $X_{ij} = 0$ if Usual Care) for participant ij , T_{ijk} is the study weeks for participant ij at time point k ($T_{ij1} = 0$ and $T_{ij2} = 12$), $I(\cdot)$ is an indicator function returning 1 (0) if the event is true (false), \mathbf{W}_{ij} is a vector of baseline measures, including the stratification factors, for participant ij , β 's and γ are regression parameters for the fixed effects, θ_i and α_{ij} are the regression parameters for the random effects for recruitment site i and participant ij , respectively, and ε_{ijk} is the random error for participant ij at time point k . Model diagnostics will be conducted to examine the assumption of normality. If there are potential violation of the assumptions, transformations of the data beginning with a log transformation will be explored. The primary efficacy estimand is the contrast of PCST and Usual Care for the change at the 12-week time point; i.e., β_3 . Differences in changes, their 95% confidence intervals, and p-values will be presented.

Question 2 (Table 10.1): Does a PCST intervention consisting of weekly, live, coach-led sessions for 12 weeks followed by IVR for 12 weeks improve outcomes at 24 weeks?

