10.2.2.3. Missing Data

If missing data are unavoidable, they will be addressed by 1) using models that are valid under the missing at random assumption, and 2) performing sensitivity analyses. The generalized linear mixed effects models are valid under the missing at random assumption. The extent and patterns of missing data will be examined, and logistic regression models will be used to identify factors associated with the missingness. Several approaches will be conducted to address the missingness. First, the generalized linear mixed effects models will further adjust for the identified factors associated with the missingness, compensating for potential violation of the missing at random assumption. Second, the propensity of the missingness, calculated from the above logistic regression, can be used to create inverse weighting in the generalized linear mixed effects models. Sensitivity analyses under missing not at random assumptions (e.g. pattern mixture models) will be conducted to examine the robustness of model-based results.⁶³ For time to event analyses, competing risk models such as cause-specific hazards models or sub-distribution hazards models will be used when there are competing events (e.g., death).

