10.2.3. Planned Interim Efficacy and Futility Analyses for the Phase 1 Randomization

Prior to trial completion, only the DSMB and a designated study statistician from the SDRC will have access to data with unblinded randomization assignments. During each interim look, the DSMB could recommend early trial termination due to efficacy or futility of the primary objective or any operational inadequacy as follows.

1. Efficacy: strong evidence is found for the primary hypothesis, indicating that a significant difference in changes in BPI Interference scores between PCST and Usual Care at Week 12 is likely to be concluded, resulting in a decision to stop the trial for superior efficacy.

2. Futility: weak evidence is found for the primary hypothesis, indicating a significant difference in changes in BPI Interference scores between PCST and Usual Care at Week 12 is unlikely to be concluded, resulting in a decision to stop for futility.
3. Operational inadequacy: failure to obtain success in the implementation of the trial such as slow recruitment, poor retention, improper data handling, or inability to implement the protocol.

For Phase 1 of the trial, one interim analysis is planned at 50% information time. However, the DSMB may request additional interim analyses and therefore a plan for an interim analysis with two looks at 50% and 75% information time is also provided. The 50% and 75% information times are defined as the times at which the randomized participants #320 and #480, respectively, have completed the Week 12 visit.

Interim Analysis with One Look at 50% Information Time. To accommodate the additional interim look, a spending-function approach⁶⁴ will be used to determine stopping bounds for efficacy and futility. For efficacy, an alpha-spending function is chosen to resemble the O'Brien-Fleming bounds.⁶⁵ For futility, a beta-spending function is chosen to select a bound that approximates a conditional power of 20% or below. Stopping boundaries are depicted in Table 10.3 for a power of 90% and a two-sided type 1 error of 5% for an interim analysis with one look at 50% information time. At the 50% information time, if the test statistic for the primary objective, i.e., regression coefficient β_4 divided by its standard error, is less than -2.89 (greater than -0.97), the trial will stop for efficacy (futility).

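### Section 10.6 appears to fill a missing Week 12 BPI Interference score with baseline, which conflicts with the missing-at-random mixed model of 10.2.2.3, and nothing says which rule governs the primary analysis

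*Combined protocol and SAP*

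**What the plan says.** Section 10.6 defines the intent-to-treat approach for Phase 1 and then gives a general rule: "For participants with missing outcome ascertainment due to withdrawal or other reasons, data from earlier assessments will be used". It illustrates the rule with the primary objective: "For example, for the primary objective for Phase 1, if Week 12 outcome data are not available, baseline data will be used". Neither sentence is described as a sensitivity analysis.

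Section 10.2.2.3 (Missing Data) takes another route. Missing data are to be handled by "using models that are valid under the missing at random assumption", with further adjustment for predictors of missingness and inverse weighting. It adds: "Sensitivity analyses under missing not at random assumptions (e.g. pattern mixture models) will be conducted". It mentions no single-value fill-in.

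The primary model in 10.2.2.1 has no imputation step: "All repeated measures of the BPI Interference scores at baseline and 12 weeks will be included in the model as the dependent variable". The power calculation in 10.2.1 takes attrition off the sample size; it reaches its number per arm "after taking into account the design effect (1.574), the attrition rate (0.2) and the inflation factor of the interim analysis (1.173").

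**The concern.** If the baseline score is entered as the Week 12 score, the participant's change is exactly zero. That is a strong assumption about what happened to people who left, and it differs from the MAR assumption the plan adopts elsewhere. It also makes the filled dataset look complete, so within that dataset the weighting and not-at-random analyses of 10.2.2.3 have no missing score to work on.

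The choice reaches the primary estimate, its confidence interval and the interim test. At the 50% look, if the statistic "is less than -2.89 (greater than -0.97), the trial will stop for efficacy (futility"), so the same data could fall on different sides of a boundary depending on which section the statistician follows. Section 10.6 plans a check on dropout ("comparisons of withdrawal rates and/or time to withdrawal will be performed as an ancillary analysis"), but that would only reveal an imbalance; it would not correct the estimate. Differential dropout is plausible here: assignment is unmasked and only PCST carries weekly sessions.

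**Working it through.** **Inputs from the documents.** 640 participants, 320 per arm; 20% attrition; SD of change 2 or 3; interim inflation factor 1.173; two-sided 5%; 90% power; example changes of 0 / -0.62 and -0.40 / -1.02 (Usual Care / PCST), all from 10.2.1 and 10.2.2; futility bound -0.97 (10.2.3).

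**Assumed, not in the documents.** Arm-specific dropout rates, a 10% dropout case, a common improvement of 1.0 point, and dropout unrelated to outcome within arm (so that an observed-data analysis is unbiased).

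**Step 1: reproduce the plan's figure.** With ICC 0, n per arm = 320 × 0.8 / 1.173 = 218. The minimum detectable difference is SD × √(2/218.2) × (1.960 + 1.282) = 0.62 at SD 2 and 0.93 at SD 3, as in Table 10.2, row 2. The power table is not in dispute. It removes non-completers, which fits an observed-data analysis; under a fill-in all 320 per arm would have a Week 12 value.

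**Step 2: formulas.** For an arm with dropout d and true mean change μ:
- fill-in mean = (1 − d)μ; variance = (1 − d)SD² + d(1 − d)μ²; n = 320
- observed-data mean = μ; variance = SD²; n = 320(1 − d)

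The results below use ICC 0 and a fixed-sample test (no interim deflation).

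**Step 3: equal 20% dropout, changes 0 / -0.62, SD 2.**
- Fill-in estimate: 0.8 × (-0.62) = -0.496.
- Fill-in variances: PCST 0.8 × 4 + 0.2 × 0.8 × 0.62² = 3.2615; Usual Care 3.2. SE = √(6.4615/320) = 0.142.
- Observed-data SE = 2 × √(2/256) = 0.177. With complete data it would be 2 × √(2/320) = 0.158.
- Coverage of -0.62 by the fill-in 95% interval: 86% (91% at SD 3; 93% at 10% dropout).
- Power: 94% under either rule.

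A simulation of 20,000 trials agreed: mean estimate -0.496, empirical SD 0.141, mean SE 0.142, coverage 86.1%. The reported SE matches the true spread, so the under-coverage comes mainly from the shift in the estimate.

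**Step 4: changes -0.40 / -1.02, SD 2.** The futility column is the chance of crossing -0.97 at the first look, with 160 per arm.

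| Dropout PCST / Usual Care | Fill-in estimate (true -0.62) | Power, fill-in v observed | Futility, fill-in v observed |
|---|---|---|---|
| 20 / 20 | -0.50 | 93% v 94% | 7.0% v 6.6% |
| 22 / 18 | -0.47 | 90% v 94% | 9.1% v 6.6% |
| 25 / 15 | -0.43 | 84% v 94% | 13.1% v 6.6% |
| 15 / 25 | -0.57 | 98% v 94% | 3.4% v 6.6% |

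For example, 25/15 gives 0.75 × (-1.02) − 0.85 × (-0.40) = -0.765 + 0.340 = -0.425. At SD 3, 25/15 gives power 51% v 65% and futility 33% v 25%. At 10/30 the fill-in overstates the effect: -0.918 + 0.280 = -0.638.

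**Step 5: no true effect, dropout 25/15, SD 2.** With a common improvement of 0, 0.40 or 1.0 point, the fill-in shifts the difference by 0, 0.04 or 0.10 against PCST. Two-sided type I error is 5.0%, 5.9% or 10.6% (SD 3: 5.0%, 5.4%, 7.5%), and false benefit for PCST is 2.5%, 1.2% or 0.4%. With 15/25 the direction reverses, and false benefit is 2.5%, 4.7% or 10.2%.

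**The case against.** The best defence is that 10.6 concerns populations, not imputation. Its first sentence includes all available data on everyone randomized, so the disputed sentence may only confirm that a participant without Week 12 stays in the model through the baseline row. It never speaks of carrying forward, imputing or a zero change. On that reading the conflict disappears, and 10.2.1, 10.2.2.1 and 10.2.2.3 all point to an observed-data analysis as the intent.

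This reading is possible but not the natural one. Baseline enters the model for every participant, so a rule conditional on Week 12 being unavailable would add nothing; and the sentence before it offers earlier data as the remedy for a missing outcome. Even if the benign meaning was intended, the wording permits the other.

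Several points on weight do stand:
- Weighting and pattern-mixture analyses could still be run on the unfilled data, so the two sections could coexist if one were declared primary.
- Under equal 20% dropout the effect on power, type I error and futility is negligible.
- The larger figures depend on assumed dropout and on scenario: with changes 0 / -0.62, power at 25/15 is about 90% rather than 84%; with 22/18 dropout and a common 1.0-point improvement, type I error is 5.9%; at ICC 0.02 (design effect 1.574) the 10.6% falls to about 8.5%.
- The observed-data comparator is a completers' change-score test, not the full mixed model. The gap is probably small.

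**Conclusion.** The concern holds. As worded, 10.6 most naturally prescribes baseline carried forward for the primary analysis, 10.2.2.3 prescribes a MAR mixed model, and the plan does not choose between them. At the plan's own attrition the choice changes the estimated effect by a fifth and the SE from 0.177 to 0.142, without a material change in power. With unequal dropout it can bias the estimate in either direction and change power, futility crossing and type I error, to a degree that depends on rates the documents do not give. All of this is bias relative to MAR, the plan's own assumption; if those who leave truly go back to their baseline score, the fill-in is right and the bias is gone. Table 10.2 is unaffected. It should be fixed, because the rule for the primary analysis should not be left to be chosen once data are in hand.

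**What to change.** Delete or reword the last two sentences of the first paragraph of 10.6. State there and in 10.2.2.3 that the primary analysis and the interim test use the mixed model on observed scores under MAR, that a missing Week 12 score is left missing, and that such participants contribute their baseline row only. If baseline carried forward is wanted, list it in 10.2.2.3 as a named missing-not-at-random sensitivity analysis. The cost is SAP wording only; no new data are needed.

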Description of Sites/Facilities Enrolling Participants	
Participants are enrolled from multiple dialysis units affiliated with the following 8 Clinical Centers, some of which involve collaborations across multiple medical centers:
 
• Hennepin Health Care• Massachusetts General Hospital• New York University• University of Illinois-Chicago• University of Pittsburgh; University of Pennsylvania• University of Washington; University of New Mexico; Rogosin Institute• Vanderbilt University Medical Center; West Virginia University• Yale University; Multiple Veterans Affairs Healthcare Systems 
The Scientific and Data Research Center is based at the University of Pennsylvania.

Description of Study Intervention	
1. Pain Coping Skills Training (PCST): Participants will complete a structured, standardized, interactive program designed to reduce pain interference, opioid use, and comorbid symptoms of depression, anxiety, and sleep disturbance. The program is adapted for the hemodialysis patient population, and is delivered using live coaches via video telehealth and with interactive voice response via telephone.2. Usual Care: Participants will be given educational materials and resources about alternatives to opioid pain medications. These materials will also be provided to participants in the PCST group.3. Buprenorphine: In a second phase of the trial, participants in both the PCST and Usual Care groups who meet eligibility criteria, including use of moderate to high-dose prescribed opioid therapy, will be offered buprenorphine as an alternative to a full-agonist opioid pain medication.
Study Duration	44 months
Participant Duration	36 weeks

[figure not shown]

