6.3. Usual Care

Participants in the Usual Care arm will be provided with written educational material about chronic pain and opioid medications, and available resources for treatment. Information will also be provided to the participant's treating clinicians that describes the trial and indicates the participant's randomized assignment. The same participant and prescriber informational materials will be used for the PCST intervention. Participants randomized to Usual Care will be assessed for eligibility for the Buprenorphine intervention at Week 24 using the same approach as for participants randomized to the PCST intervention.

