6.4. Intervention Fidelity

Throughout the duration of the trial, the fidelity of the interventions will be monitored through ongoing review of both participant adherence and research team implementation. Efforts to maximize adherence will be implemented by the Clinical Center research teams with guidance and assistance from the trial's Quality Control Committee.

For the coach-led telehealth component of the PCST intervention, adherence will be based on the number of telehealth sessions completed (out of 12 prescribed sessions) and categorized as minimal (< 3 session), some (3-9 sessions), and most (10-12). Additional adherence data will include the duration of sessions, completion of PCST homework, utilization of symptom management skills, and utilization of opioid reduction strategies. For the IVR component of the PCST intervention, the proportion of calls completed and duration of IVR will be indicators of adherence.

To ensure that the PCST intervention is delivered as intended there will be regular interactions between coaches and the relevant supervisory team, during which implementation and clinical issues will be reviewed. For each coach, the audio recordings of all PCST sessions for a minimum of one participant will be reviewed to provide ratings for treatment fidelity using forms that capture the core skills and intervention components. In addition to the review of all sessions for a minimum of one participant per coach, a random sample of subsequent telehealth sessions will be reviewed and scored for fidelity to the intervention. This will allow coaches to receive support and real-time feedback to ensure the highest standards for delivering the intervention. Ongoing supervision for the IVR component will also be provided during weekly meetings. Enactment fidelity, i.e., the degree to which participants implement and use the intervention skills, will be assessed post-treatment by the coach using a checklist.

For the buprenorphine intervention, participants who meet eligibility criteria will be encouraged, but not required, to initiate buprenorphine. The proportion of participants offered the drug who initiate buprenorphine is one of the exploratory outcomes for the intervention. Rates of completion of the structured follow-up contacts and subsequent monthly contacts will serve as indicators of implementation fidelity.

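### The as-treated and all-treated sets in 10.6 can in practice move or drop only PCST participants, so PCST versus Usual Care comparisons in them are open to selection bias of unknown direction

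*Combined protocol and SAP*

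**What the plan says.** Section 10.6 makes ITT the approach for the Phase 1 questions: "analyses will use an intent-to-treat (ITT) approach, in which all available data on all randomized participants are included". It then adds three further sets, introduced by "Other populations that may be used in secondary analyses are defined as follows". Two matter here. For the as-treated set, "As-treated participants will be analyzed according to the study intervention actually received". The all-treated set is "Any participant randomized into the study that received at least some of the study intervention". Neither definition gives a threshold for receipt, says what receipt means in Usual Care, or provides an adjustment for selection. The third set, per-protocol, is not part of this point.

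Usual Care (6.3) is written material for the participant plus information for the treating clinicians. The same section says of the PCST arm: "The same participant and prescriber informational materials will be used for the PCST intervention". The synopsis agrees: "These materials will also be provided to participants in the PCST group".

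Session attendance exists only in PCST. Section 6.4 counts completed telehealth sessions out of 12, "categorized as minimal (< 3 session), some (3-9 sessions), and most (10-12"). Section 10.6 does not refer to these categories.

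**The concern.** A PCST participant who attends no session by Week 12 has, in terms of study material, received what a Usual Care participant receives. The as-treated rule would then analyse that person as Usual Care. The reverse move has no described path. Under the all-treated rule the same person would be dropped if receipt means a session, while the comparable Usual Care participant, who would not have attended either, stays in. Non-adherence can be seen and acted on in one arm only, so the two groups no longer have the same mix of would-be starters and non-starters.

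Apart from per-protocol, these are the plan's only populations for asking what PCST does for people who take it up. A difference found in them could come entirely from who starts, and could be taken as supporting the ITT result.

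**Working it through.** **Inputs from the documents.** 640 participants, hence 320 per arm; SD of change 2; two-sided 5% test; 20% attrition, hence 256 per arm (10.2.1, 10.2.1.1, 10.2.2).

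**Assumed inputs, because the documents give neither.** q is the share of non-starters, taken as 10% or 15%. g is how much worse their change in BPI Interference is than that of starters, whichever arm they are in, taken as 0.5 or 1.0 point.

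**The plan's own figure, for scale.** With ICC 0 the effective size per arm is 320 × 0.8 / 1.173 = 218.2. The detectable difference at 90% power is about (1.96 + 1.28) × 2 × √(2/218.2) = 0.62, which matches Table 10.2, row 2.

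**Bias with no true effect.** Set the starters' mean change to 0. The Usual Care arm then has mean qg.

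- All-treated, if receipt means a session: PCST keeps starters only (mean 0) against Usual Care (mean qg). The apparent benefit is qg.
- As-treated: starters (mean 0) against N Usual Care participants plus qN moved non-starters. The apparent benefit is (Nqg + qNg)/(N + qN) = 2qg/(1 + q).
- All-treated, if the shared materials count as receipt: nobody is dropped on these grounds and the bias is 0.

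**Standard errors.** All-treated: 2√[1/(N − qN) + 1/N]. As-treated: 2√[1/(N − qN) + 1/(N + qN)]. With b the bias and s its standard error, the false-positive rate is Φ(−1.96 − b/s) + 1 − Φ(1.96 − b/s).

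**Worked case, N = 320, q = 0.10, g = 1.** All-treated: b = 0.10, s = 2√(1/288 + 1/320) = 0.162, rate 9.4%. As-treated: b = 0.2/1.1 = 0.18, s = 2√(1/288 + 1/352) = 0.159, rate 20.8%.

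| Per arm | g | q | Bias, all-treated / as-treated | False-positive rate, all-treated / as-treated |
|---|---|---|---|---|
| 320 | 0.5 | 10% | 0.05 / 0.09 | 6.1% / 8.8% |
| 320 | 0.5 | 15% | 0.075 / 0.13 | 7.4% / 12.9% |
| 320 | 1.0 | 10% | 0.10 / 0.18 | 9.4% / 20.8% |
| 320 | 1.0 | 15% | 0.15 / 0.26 | 14.9% / 37.1% |
| 256 | 1.0 | 10% | 0.10 / 0.18 | 8.5% / 17.6% |
| 256 | 1.0 | 15% | 0.15 / 0.26 | 12.9% / 30.9% |

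If the plan's design effect of 1.574 is also applied (256/1.574 = 162.6 effective per arm), the case q = 10%, g = 1 falls to 7.2% / 12.9%.

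**Sign.** Both formulas are proportional to g. At g = 0 the bias is zero and the rate is 5%. At g below 0 the bias has the same size and runs against PCST. Simulation (4,000 trials, 256 per arm, q = 20%) agrees. Non-starters 1.0 worse give 0.20 and 0.33 in favour of PCST, no difference gives 0 and 0, and 1.0 better gives 0.20 and 0.34 against it.

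**The case against.** **Direction.** A reader might infer that these sets are biased towards PCST. The documents do not establish that. Movement between groups is one-way, but the sign of the bias depends on non-starters' prognosis, on which they are silent. There are hints: 2.2.5.2 links depressive symptoms to hospitalisation and to non-adherence with dialysis, and 8.1 expects hospitalisation to interrupt PCST. But the endpoint is change from baseline, and being sicker does not by itself mean a worse change. This objection stands, so the direction stays open.

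**All-treated.** A reader might also infer that this set certainly drops PCST non-starters. That is only one reading. Since the materials go to PCST participants too, they may count as receipt, and the set then equals ITT. This stands as well: the defect is an undefined term, and neither reading yields a useful adherence analysis.

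**Size.** A deficit of 1.0 point is half the SD and equals the individual minimal important change cited in 10.2.1.1, so the upper rows of the table are demanding cases. Section 10.6 also replaces a missing Week 12 value with baseline. If non-starters, and their Usual Care counterparts, all miss Week 12, g becomes the average improvement of everyone else. With the illustrative Usual Care decrease of 0.40 in 10.2.1, the rates at 320 per arm are only 5.7% / 7.4% (q = 10%) and 6.5% / 10.0% (q = 15%). With the other illustration there, a change of 0, there is no bias. The range must therefore be shown, not one figure.

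**Scope.** The sets are optional, no specific analysis is assigned to them, and the Phase 1 analyses are ITT. That limits the importance of the point without removing it. In addition, attending no telehealth session need not mean receiving no PCST after Week 12, because nothing described bars such a participant from the IVR phase. The argument is cleanest at Week 12.

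**Conclusion.** The point holds as a structural one. In the as-treated set, reclassification can in practice go only from PCST to Usual Care. The all-treated set is either one-sided in the same way or redundant with ITT. Neither comparison keeps the protection of randomisation, and the plan offers no adjustment.

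The bias is zero if non-starters and starters would have changed alike, and takes either sign otherwise. For 10% to 15% non-starters who do 0.5 to 1.0 point worse, it is 0.05 to 0.15 points (all-treated, session reading) and 0.09 to 0.26 points (as-treated), against a stated detectable difference of 0.62. The corresponding false-positive rates at 320 per arm are about 6% to 15% and 9% to 37%, and lower after attrition. All of this rests on assumed values of q and g.

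A reader should not take this as casting doubt on the primary result: the ITT comparison does not use these sets.

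**What to change.** In 10.6, do not use the as-treated and all-treated sets to estimate PCST versus Usual Care effects. Delete them, or label them descriptive and state how receipt is defined in each arm, including for PCST participants who received only the materials.

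For the adherence question at Week 12, specify a complier average causal effect with randomised arm as the instrument. Define uptake as at least 3 telehealth sessions, the boundary above the lowest category in 6.4. As a sensitivity version, use the number of sessions, 0 to 12. With no access to coaches in Usual Care, the threshold estimate is in essence the ITT difference divided by the share of the PCST arm reaching 3 sessions. With no effect of assignment the numerator is centred on zero whatever the prognosis of non-starters.

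State the assumptions:

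- Assignment affects the outcome only through sessions. This is open to question, because participants are unmasked and report the outcome themselves, and treating clinicians are told the assignment (4.1, 6.3).
- Threshold version: fewer than 3 sessions has no effect.
- Session-count version: the effect is linear in sessions. This replaces the threshold assumption and does not test it.

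The cost is a short change to the SAP text and one two-stage model on session counts already collected for fidelity. The price is a wider interval than the as-treated one and reliance on assumptions that the data cannot verify.
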